13.3 Pregnancy Test

A null listing will be presented for pregnancy test results , as this will not be applicable for patients in this study.

13.4 Vital Signs

Vital signs will be collected at Day 1 and Day 14 of each treatment. Baseline vital signs will be determined as those at Day 1 for each treatment.

The result and change from baseline of each treatment in vital signs parameters (systolic and diastolic blood pressure, pulse and temperature) will be listed and summarized descriptively for each scheduled time-point during the study.

13.5 Physical Examination

Physical examinations data will be listed.

Visit dates will be listed.

14 Palatability

At the end of each of the two treatment cycles patients (together with their parents) will be surveyed using a standard questionnaire for their views of the palatability and acceptability of the 13-CRA. In the case of patients <6 years of age, the researcher will survey the view of one or both parents. For patients from 6 years of age, the researcher will seek the views of one or both parents and the patient.

The questionnaire will probe the taste and general acceptability (willingness to continue with treatment, ease of dose administration etc.). After five patients have completed the survey the use of the questionnaire will be reviewed, by both the investigator and Nova, to ensure that it is working satisfactorily.

Data on the following will be collected using a visual (hedonic) analogue scale and verbal responses:

- Taste on first administration
- Residual after taste
- Smell
- Any incidences of spitting medicine out or vomiting
- Willingness to take 13-CRA on a daily basis
- Ease of dose administration using the bottle and oral syringe
- Preference between extracted capsule and liquid medicines

All palatability data will be listed. Each question recorded on a VAS scale will be summarised by treatment, presenting summary statistics for the length of line. Each categorical question will be summarised by treatment, presenting frequency counts and percentages

15 Interim Analysis

There is no planned interim analysis.

16 Changes to Planned Methodology

It was planned in the protocol to summarise tables by age group (1-11 years, 12-<21 years). However as all patients in the study were under 12, all patients were summarised together in a "total" treatment group.

17 Tables, Figures and Listings

Tables and listings will be presented landscape. A font size of 8 and a font of courier new will be used throughout for tables and listings. Tables and listings will be provided as a bookmarked pdf. Figures will be provided as individual files.

The patient subset being utilized in the table will be indicated in the table title. Page numbers and dates of production will be included in an appropriate place at the bottom of the output. Listings which support the table will also be detailed in an appropriate place at the bottom of the output.

Tables will only be generated where there is sufficient data to warrant the inclusion of the table.

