5.2 Secondary Endpoints

Safety parameters:

- Evaluate the local (oro-pharyngeal) tolerability
- Skin toxicity
- Hypercalcaemia (noted as adverse events if intervention required)
- Hepatotoxicity (noted as adverse events if intervention required)
- Triglycerides (noted as adverse events if intervention required)

Palatability and acceptability parameters:

- Evaluate the taste acceptability of the new oral formulation of 13-CRA

6 Study Design

This is an open label, randomised, multiple dose, cross-over relative bioavailability and PK trial of oral 13-CRA liquid administered to patients aged from 0- < 21 years. The decision to initiate 13-CRA therapy will be taken independently of the trial protocol. The trial will be conducted in patients who are attending the hospital for treatment for neuroblastoma requiring at least two cycles of 13-CRA. 13-CRA will be prescribed to patients according to the locally approved treatment protocols at a dose of 200mg/m²/day for both test and reference product. Oral 13-CRA is administered for neuroblastoma (NBL) (this is usually at a dose of 160mg/m²) for 14 days, every 4 weeks, for 6 months, however where the dose is extracted from capsules this dose is increased to 200mg/m². In this trial the dose of 13-CRA will be 200mg/m² as patients able to swallow the capsules will not be recruited to the trial. Patients with a body weight of ≤12kg will receive a dose of 160 mg/m². Patients who require their dose through a nasogastric tube or gastrostomy will be included in the trial, this will be recorded in the case record form.

Evaluation of the test and reference product will occur during two months of therapy.

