7.2 Randomisation

Prior to the initiation of the trial 13-CRA, patients will be randomised to receive either liquid or extracted capsule formulation in “My –CRA month 1”. The patients will then cross-over to the alternative formulation in “My-CRA month 2”. After the trial if a patient requires additional cycles of 13-CRA, the patient will revert to standard 13-CRA therapy i.e. extracted capsules according to local practice.

Randomisation will be done centrally by Nova according to a randomisation list generated by the trial statistician, investigators will email (or telephone) Nova to receive randomisation details, this will be confirmed by email as “liquid first” or “extracted capsules first”, pharmacy contacts will also be notified.

8 Major Protocol Deviations

Protocol violations are any deviations from the procedures outlined in the protocol, for example, missed evaluations, incorrect timing of evaluations, non-compliance with investigation medical product (IMP) and intake of prohibited medications. It is the investigator’s responsibility to make all reasonable efforts to avoid protocol violations in order to avoid possible exclusion of the patient from the trial and/or analyses.

Major protocol deviations are defined as those deviations from the study protocol that may have the ability to impact the study results.

Major protocol deviations include (but are not limited to):

- Deviation from inclusion/exclusion criteria
- Withdrawal criteria met during the study but patient was not withdrawn
- Missed evaluations
- Incorrect timing of evaluations
- Prohibited concomitant medications
- Non-compliance with IMP

Where possible; major deviations will be programmatically generated. Listings of concomitant medications will be provided to the sponsor for review to identify prohibited medications prior to database freeze.

Major protocol deviations will result in exclusion from the pharmacokinetic population if they are considered likely to affect the determination of the pharmacokinetic parameters.

9 Analysis Populations

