9.2 Safety Population

The safety population is defined as all patients who receive trial medication. This population is the primary population for all safety summaries.

10 Data Reporting Conventions

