10.1 Descriptive Statistics

Unless otherwise stated, all continuous parameters will be summarized using standard summary statistics as appropriate (n, mean, standard deviation [SD], coefficient of variation [%CV], minimum, median and maximum). Summary statistics for categorical variables will include frequency counts and percentages.

In the presentation of descriptive summary statistics, the minimum and maximum will be presented to the same number of decimal places as the variable being reported. The mean and median will be reported to one extra decimal place; the SD to two extra decimal places.

Frequency counts will be provided for categorical variables (e.g., gender). Unless otherwise stated, this will consist of the number of patients in a particular category and the percentage of the total number of patients per dose group, presented to one decimal place.

Analyses will be performed using the validated statistical software SAS version 9.4 or higher.

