17.1 List of Tables

Table Number	Table Title	Population
Table 14.1.1	Patient Disposition	Safety Population
Table 14.1.2	Major Protocol Deviations	Safety Population
Table 14.1.3	Demography	Safety Population
Table 14.1.4	Oncology Medical History	Safety Population
Table 14.1.5	Non-Oncology Medical History	Safety Population
Table 14.1.6	Prior Medications	Safety Population
Table 14.1.7	Concomitant Medications	Safety Population
Table 14.2.1	Summary of 13-CRA Plasma Concentrations	PK Population
Table 14.2.2	Summary of 4-oxo-13-cis-RA Plasma Concentrations	PK Population
Table 14.2.3	Summary of 13-CRA Pharmacokinetic Parameters	PK Population
Table 14.3.1	Study Drug Exposure	Safety Population
Table 14.3.2.1	Overall Adverse Event Summary	Safety Population
Table 14.3.2.2	Treatment Emergent Adverse Events by System Organ Class and Preferred Term	Safety Population
Table 14.3.2.3	Treatment Emergent Adverse Events by System Organ Class, Preferred Term and Maximum Severity	Safety Population
Table 14.3.2.4	Treatment Emergent Adverse Events by System Organ Class, Preferred Term and Strongest Relationship	Safety Population
Table 14.3.2.5	Treatment Emergent Serious Adverse Events by System Organ Class and Preferred Term	Safety Population
Table 14.3.2.6	Treatment Emergent Serious Adverse Events by System Organ Class, Preferred Term and Maximum Severity	Safety Population
Table 14.3.2.7	Treatment Emergent Serious Adverse Events by System Organ Class, Preferred Term and Strongest Relationship	Safety Population

Table Number	Table Title	Population
Table 14.3.2.8	Oro-pharyngeal Tolerability	Safety Population
Table 14.3.3	Summary of Result and Change from Baseline Value for Vital Sign Parameters	Safety Population
Table 14.3.4	Summary of Palatability Questions	Safety Population

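### SAP section 14 and Table 14.3.4 summarise cross-over palatability ratings by treatment only; a descriptive summary of the within-patient difference should be added

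*SAP*

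**What the plan says.** SAP section 6 describes the design: "This is an open label, randomised, multiple dose, cross-over relative bioavailability and PK trial of oral 13-CRA liquid". On the second cycle, SAP section 7.2 says: "The patients will then cross-over to the alternative formulation". SAP section 14 then sets the timing of the ratings: "At the end of each of the two treatment cycles patients (together with their parents) will be surveyed using a standard questionnaire". The design therefore yields up to two sets of ratings per patient, one per product.

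The analysis text in SAP section 14 has two parts. For visual analogue items: "Each question recorded on a VAS scale will be summarised by treatment, presenting summary statistics for the length of line". For the rest: "Each categorical question will be summarised by treatment, presenting frequency counts and percentages". SAP section 10.1 gives the general rule that "all continuous parameters will be summarized using standard summary statistics as appropriate", and lists n, mean, SD, %CV, minimum, median and maximum. It lists no difference and no confidence interval.

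SAP section 17.1 has one palatability table, 14.3.4, titled "Summary of Palatability Questions", on the Safety Population. SAP section 9.2 defines that population: "The safety population is defined as all patients who receive trial medication". Having rated both products is not required. Protocol section 8.1 keeps data collected before withdrawal unless the family asks otherwise, and SAP section 10.2 imputes nothing beyond partial dates. Protocol section 11.2 leaves the palatability summary unspecified.

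Two features keep the pairing in view. Listing 16.2.9.4 holds all palatability data, and SAP section 17.3 sorts listings by sequence, patient and treatment. The questionnaire also asks which of the two products is preferred.

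**The concern.** Palatability and acceptability form a secondary objective, and Protocol section 1 offers better palatability for children as one reason for the liquid. Surveying both cycles and asking for a preference invite a comparison, so readers will set the two columns of Table 14.3.4 side by side.

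With at most 20 patients, the main strength of these data is that each patient acts as his or her own control. Column means and SDs do not show that. A reader who wants to judge the precision of the contrast would have to treat the columns as two separate groups or rebuild the pairs by hand from the listing. A patient surveyed after one cycle only enters one column, so the columns need not describe the same patients.

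**Working it through.** The documents state no SD, effect size, correlation or power for palatability (SAP section 7.1 says there are no power calculations), so there is no planned figure to reproduce. The size below is illustrative.

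**Inputs from the documents.** 12 to 18 patients hoped for and up to 20 allowed (SAP section 7.1); two ratings per patient (SAP section 14).

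**Inputs assumed.** Correlation ρ of 0.3, 0.5 or 0.7 between a patient's two ratings; equal SD for both products; for the millimetre example, SD 25 mm and 16 patients.

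**1. What the columns can and cannot give.** With complete pairs, mean(liquid) − mean(capsule) = mean(liquid − capsule), so the point estimate is recoverable. The SD of the difference is SD × √(2(1 − ρ)), and ρ is not in the table. For ρ = 0.3, 0.5, 0.7 it is √1.4 = 1.18, √1.0 = 1.00 and √0.6 = 0.77 times the SD of a single rating. Nor do the columns show how many patients scored the liquid higher.

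**2. Standard error of the difference.** Two-group reading: SD × √(2/n). Paired: SD × √(2(1 − ρ)/n). The ratio of paired to two-group is √(1 − ρ), whatever the SD and n: 0.84, 0.71 and 0.55, a reduction of 16%, 29% and 45%. At ρ = 0 the ratio is 1.

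| n | Two-group | Paired, ρ = 0.3 | ρ = 0.5 | ρ = 0.7 |
|---|---|---|---|---|
| 12 | 0.408 SD | 0.342 SD | 0.289 SD | 0.224 SD |
| 20 | 0.316 SD | 0.265 SD | 0.224 SD | 0.173 SD |

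**3. The same in millimetres (SD 25 mm and n = 16, both assumed).** The two-group 95% half-width is t(0.975, 30) × 25 × √(2/16) = 18.1 mm. The paired half-width is t(0.975, 15) × 25 × √(2(1 − ρ)/16) = 15.8, 13.3 and 10.3 mm for ρ = 0.3, 0.5 and 0.7.

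**4. One-product raters.** Suppose m of the N raters in one column never rated the other product, and their mean lies b away from that of the paired patients. That column mean, and hence the column difference, moves by (m/N) × b. With m = 2, N = 20 and b = 10 to 30 mm, the shift is 1 to 3 mm. With m = 4 and N = 12, it is 3.3 to 10 mm. All values of m and b are assumed; the documents do not say how many such patients there are.

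**5. Period.** Write δ for the period 1 minus period 2 effect. The liquid-minus-capsule difference then carries +δ in the liquid-first sequence and −δ in the other. The pooled mean carries δ × (n₁ − n₂)/(n₁ + n₂), where n₁ and n₂ are the numbers with both ratings in the liquid-first and capsule-first sequences. This is zero when the sequences are equal in size and not otherwise.

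**The case against.** The strongest reply is that nothing comparative was promised. The objective is to assess palatability, the endpoint in SAP section 5.2 is worded for the liquid alone, and no test or interval is planned. The two-group interval in the working is a reader's construction and appears nowhere in the SAP. That stands, and it keeps this point minor. It does not remove it: the plan collects and tabulates both products, and what is missing is itself descriptive.

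A reader might infer that the cross-over pairing is lost, or that the columns can only be read as independent groups. The documents do not support that. The listing keeps each pair together, the preference item is a within-patient comparison, and with complete data the column means give the right mean difference. What is missing is the paired summary.

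A reader might also infer that the comparison is biased by drop-out. No one-product raters are documented, and each column will show its own n, so an imbalance would be visible. This is a possibility of unknown size.

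A blanket paired analysis would not fit every item. The preference item is already comparative. The ease-of-administration item is worded around the bottle and oral syringe, so a contrast with the capsule may mean little. From age 6, parent and patient may both answer. Protocol section 4.8 allows the questionnaire to be adjusted after five patients. These points stand and shape the fix.

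**Conclusion.** The point holds as a minor gap in presentation and precision. The planned table omits the spread and confidence interval of the within-patient difference and the count favouring each product, none of which can be derived from the columns. The 16% to 45% gain in standard error rests on an assumed correlation of 0.3 to 0.7. The millimetre figures rest further on an assumed SD and number of patients. The effect of one-product raters cannot be sized from the documents. Data collection and the primary pharmacokinetic analysis are untouched.

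**What to change.** In SAP section 14 and Table 14.3.4, keep the by-treatment columns and add the following.

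- **Visual analogue items asked of both products:** the liquid-minus-extracted-capsule difference in patients with both ratings, with number of pairs, mean, SD, median, range and a 95% confidence interval labelled descriptive. Show it also by sequence, so that a period effect is visible.
- **Who forms the pair:** the same respondent type, parent or patient, in both cycles.
- **Categorical items asked of both products:** a paired cross-table of the liquid response against the capsule response.
- **Preference item:** one overall count, not split by treatment.
- **Items worded for one product:** no paired contrast.
- **Completeness:** the number of patients who rated one product only.

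The cost is a paragraph of SAP wording and one extra table panel. No new data are needed.

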17.1 List of Tables

Table Number	Table Title	Population
Table 14.1.1	Patient Disposition	Safety Population
Table 14.1.2	Major Protocol Deviations	Safety Population
Table 14.1.3	Demography	Safety Population
Table 14.1.4	Oncology Medical History	Safety Population
Table 14.1.5	Non-Oncology Medical History	Safety Population
Table 14.1.6	Prior Medications	Safety Population
Table 14.1.7	Concomitant Medications	Safety Population
Table 14.2.1	Summary of 13-CRA Plasma Concentrations	PK Population
Table 14.2.2	Summary of 4-oxo-13-cis-RA Plasma Concentrations	PK Population
Table 14.2.3	Summary of 13-CRA Pharmacokinetic Parameters	PK Population
Table 14.3.1	Study Drug Exposure	Safety Population
Table 14.3.2.1	Overall Adverse Event Summary	Safety Population
Table 14.3.2.2	Treatment Emergent Adverse Events by System Organ Class and Preferred Term	Safety Population
Table 14.3.2.3	Treatment Emergent Adverse Events by System Organ Class, Preferred Term and Maximum Severity	Safety Population
Table 14.3.2.4	Treatment Emergent Adverse Events by System Organ Class, Preferred Term and Strongest Relationship	Safety Population
Table 14.3.2.5	Treatment Emergent Serious Adverse Events by System Organ Class and Preferred Term	Safety Population
Table 14.3.2.6	Treatment Emergent Serious Adverse Events by System Organ Class, Preferred Term and Maximum Severity	Safety Population
Table 14.3.2.7	Treatment Emergent Serious Adverse Events by System Organ Class, Preferred Term and Strongest Relationship	Safety Population

Table Number	Table Title	Population
Table 14.3.2.8	Oro-pharyngeal Tolerability	Safety Population
Table 14.3.3	Summary of Result and Change from Baseline Value for Vital Sign Parameters	Safety Population
Table 14.3.4	Summary of Palatability Questions	Safety Population

17.2 List of Figures

Figure Number	Figure Title	Population
Figure 14.2.4	Individual 13-CRA Plasma Concentration-Time Curves	PK Population
Figure 14.2.5	Individual 4-oxo-13-cis-RA Plasma Concentration-Time Curves	PK Population
Figure 14.2.6	Mean 13-CRA Plasma Concentration-Time Curve	PK Population
Figure 14.2.7	Mean 4-oxo-13-cis-RA Plasma Concentration-Time Curve	PK Population

17.3 List of Listings

Listings will be sorted by treatment sequence, patient number and treatment.

Listing Number	Listing Title	Population
Listing 16.2.1.1	Patient Disposition	All Patients
Listing 16.2.1.2	Informed Consent / Randomisation	All Patients
Listing 16.2.1.3	Pre-Trial Eligibility	All Patients
Listing 16.2.1.4	Pre-Treatment Eligibility	All Patients
Listing 16.2.2	Major Protocol Deviations	All Patients
Listing 16.2.3	Population Allocation	All Patients
Listing 16.2.4.1	Demography	All Patients
Listing 16.2.4.2	Oncology Medical History	All Patients
Listing 16.2.4.3	Non-Oncology History	All Patients

Listing Number	Listing Title	Population
Listing 16.2.4.4	Prior and Concomitant Medications	All Patients
Listing 16.2.5.1	Study Drug Administration	All Patients
Listing 16.2.5.2	Overall Study Drug Exposure	All Patients
Listing 16.2.6.1	13-CRA Plasma Concentrations	All Patients
Listing 16.2.6.2	4-oxo-13-cis-RA Plasma Concentrations	All Patients
Listing 16.2.6.3	13-CRA Pharmacokinetic Parameters	All Patients
Listing 16.2.7.1	Adverse Events	All Patients
Listing 16.2.7.2	Serious Adverse Events	All Patients
Listing 16.2.7.3	Oro-pharyngeal Tolerability	All Patients
Listing 16.2.8.1	Pregnancy Tests	All Patients
Listing 16.2.9.1	Vital Signs	All Patients
Listing 16.2.9.2	Physical Examination	All Patients
Listing 16.2.9.3	Visit Dates	All Patients
Listing 16.2.9.4	Palatability Data	All Patients
